5.2 Enrollment and Retention of Study Population

5.2.1 Recruitment Procedures

Before the start of the study, the Investigator and / or study staff will determine the recruitment strategy to be used for this study (eg, advertising, database, direct mail, word of mouth referral). Using the relevant methods they will contact an appropriate pool of potential parents / guardians and invite them to participate in the study. The site will ensure that any advertisements or materials used to recruit subjects (eg, letters, pamphlets, posters, etc.) have been submitted to Sanofi Pasteur for review prior to submission to the IEC/IRB for approval.

In addition, a parent / guardian who brings a child to the study site for a routine visit will be invited to enroll the subject in the study, if eligible. Subjects may also be recruited from the general population.

5.2.2 Informed Consent Procedures

Informed consent is the process by which a subject's parent(s) / guardian voluntarily confirms his or her willingness to allow the child to participate in a particular study. Informed consent must be obtained before any study procedures are performed. The process is documented by means of a written, signed, and dated ICF.

In accordance with GCP, prior to signing and dating the consent form, the subject's parents / guardian must be informed by appropriate study personnel about all aspects of the study that are relevant to making the decision to participate, and must have sufficient time and opportunity to ask any questions.

The actual ICF used at each center may differ, depending on local regulations and IEC / IRB requirements. However, all versions must contain the standard information found in the sample ICF provided by the Sponsor. Any change to the content of the ICF must be approved by the Sponsor and the IEC / IRB prior to the form being used.

If new information becomes available that may be relevant to the subject's parent / guardian's willingness to continue participation in the study, this will be communicated to him / her in a timely manner. Such information will be provided via a revised ICF or an addendum to the original ICF.

ICFs will be provided in duplicate, or a photocopy of the signed consent will be made. The original will be kept by the Investigator, and the copy will be kept by the subject's parent / guardian.

Documentation of the consent process should be recorded in the source documents.

5.2.3 Screening Criteria

There are no screening criteria other than the inclusion and exclusion criteria.

5.2.4 Inclusion Criteria

An individual must fulfill *all* of the following criteria to be eligible for study enrollment:

Toddlers and infants

- 1) Informed consent form has been signed and dated by the parent(s) or other guardian, and by an independent witness, if required by local regulations
- 2) Subject and parent/guardian are able to attend all scheduled visits and to comply with all study procedures
- 3) Born at full term of pregnancy (≥ 37 weeks) and/or with a birth weight ≥ 5.5 lbs or 2.5 kg
- 4) Healthy toddlers / infants as determined by medical history, physical examination, and judgment of the Investigator

Specifically for toddlers

- 5) Aged 12 to 15 months on the day of the first study visit^a
- 6) Subject has received 3 doses of Prevnar 13 and 3 doses of diphtheria, tetanus, acellular pertussis, poliovirus and *Haemophilus influenzae* type b antigens in infancy

Specifically for infants

- 7) Aged 42 to 89 days on the day of the first study visit^b

5.2.5 Exclusion Criteria

An individual fulfilling *any* of the following criteria is to be excluded from study enrollment:

Toddlers and infants

- 1) Participation at the time of study enrollment (or in the 4 weeks preceding the first study vaccination) or planned participation during the present study period in another clinical study investigating a vaccine, drug, medical device, or medical procedure
- 2) Family history of congenital or hereditary immunodeficiency, until the immune competence of the potential vaccine recipient is demonstrated
- 3) Blood dyscrasias, leukemia, lymphoma of any type, or other malignant neoplasms affecting the bone marrow or lymphatic systems
- 4) Active tuberculosis
- 5) History of *S. pneumoniae* infection or disease, confirmed either serologically or microbiologically
- 6) History of any neurologic disorder, including any seizures and progressive neurologic disorders
- 7) History of Guillain-Barré syndrome
- 8) Known systemic hypersensitivity to any of the vaccine components, or history of a life-threatening reaction to the vaccines used in the study or to a vaccine containing any of the same substances
- 9) Verbal report of thrombocytopenia contraindicating intramuscular (IM) vaccination in the Investigator's opinion
- 10) Bleeding disorder, or receipt of anticoagulants in the 3 weeks preceding inclusion, contraindicating IM vaccination in the Investigator's opinion
- 11) Receipt of oral or injectable antibiotic therapy within 72 hours prior to the first blood draw
- 12) Chronic illness (including, but not limited to, cardiac disorders, congenital heart disease, chronic lung disease, renal disorders, auto-immune disorders, diabetes, psychomotor diseases, and known congenital or genetic diseases) that, in the opinion of the Investigator, is at a stage where it might interfere with study conduct or completion

^a “12 to 15 months” means from the 12th month after birth to the day before the 16th after birth

^b “42 to 89 days” means the 42nd day after birth to the day before the 90th day after birth

- 13) Any condition which, in the opinion of the Investigator, might interfere with the evaluation of the study objectives
- 14) In an emergency setting, or hospitalized involuntarily.
- 15) Moderate or severe acute illness/infection (according to Investigator judgment) on the day of vaccination or febrile illness (temperature $\geq 38.0^{\circ}\text{C}$ / $\geq 100.4^{\circ}\text{F}$). A prospective subject should not be included in the study until the condition has resolved or until 3 days after the febrile event has resolved
- 16) Identified as a natural or adopted child of the Investigator or employee with direct involvement in the proposed study

Specifically for toddlers

- 17) Receipt of any vaccine in the 4 weeks preceding the study vaccination or planned receipt of any vaccine from enrollment through the last blood sampling Visit (Visit 2), except for influenza vaccination, which may be received at least 2 weeks before or 2 weeks after any study vaccination. This exception includes monovalent pandemic influenza vaccines and multivalent influenza vaccines
- 18) Receipt of immune globulins, blood or blood-derived products in the past 3 months
- 19) Known or suspected congenital or acquired immunodeficiency; or receipt of immunosuppressive therapy, such as anti-cancer chemotherapy or radiation therapy, within the preceding 6 months; or long-term systemic corticosteroid therapy (prednisone or equivalent for more than 2 consecutive weeks within the past 3 months)
- 20) History of diphtheria, tetanus, pertussis, poliomyelitis, and/or *H. influenzae* type b infection or disease

Specifically for infants

- 21) Receipt of any vaccine in the 4 weeks preceding the study vaccination or planned receipt of any vaccine from enrollment through the last blood sampling Visit (Visit 6), except for influenza vaccination or COVID 19 vaccination, which may be received at least 2 weeks before or 2 weeks after any study vaccination. This exception includes monovalent pandemic influenza vaccines and multivalent influenza vaccines, and COVID-19 vaccines, as applicable per local recommendations.
- 22) Receipt of immune globulins, blood or blood-derived products since birth.
- 23) Known or suspected congenital or acquired immunodeficiency; or receipt of immunosuppressive therapy, such as anti-cancer chemotherapy or radiation therapy; or long-term systemic corticosteroid therapy (prednisone or equivalent for more than 2 consecutive weeks) since birth
- 24) Previous vaccination against *S. pneumoniae*
- 25) Previous vaccination against the following antigens: diphtheria, tetanus, pertussis, *H. influenzae* type b, poliovirus, rotavirus, measles, mumps, rubella, and varicella
- 26) Receipt of more than 1 previous dose of hepatitis B vaccine

27) History of diphtheria, tetanus, pertussis, poliomyelitis, hepatitis B, measles, mumps, rubella, varicella, *H. influenzae* type b, and/or rotavirus infection or disease

28) History of intussusception

If the subject has a primary physician who is not the Investigator, the site should contact this physician with the parent / guardian's consent to inform him / her of the subject's participation in the study. In addition, the site should ask this primary physician to verify exclusion criteria relating to previous therapies, such as receipt of blood products or previous vaccines.

5.2.6 Medical History

Prior to enrollment, subjects will be assessed for pre-existing conditions and illnesses, both past and ongoing. Any such conditions will be documented in the source document. Significant (clinically relevant) medical history (reported as diagnosis) including conditions/illnesses for which the subject is or has been followed by a physician or conditions/illnesses that could resume during the course of the study or lead to an SAE or to a repetitive outpatient care will be collected in the case report book (CRB). The significant medical history section of the CRB contains a core list of body systems and disorders that could be used to prompt comprehensive reporting, as well as space for the reporting of specific conditions and illnesses.

For each condition, the data collected will be limited to:

- Diagnosis (this is preferable to reporting signs and symptoms)
- Presence or absence of the condition at enrollment

The reporting of signs and symptoms in lieu of a diagnosis is strongly discouraged.

Dates, medications, and body systems are not to be recorded, and the information collected will not be coded. Its purpose is to assist in the later interpretation of safety data collected during the study.

5.2.7 Contraindications for Subsequent Vaccinations

5.2.7.1 Temporary Contraindications

Toddlers

Not applicable.

Infants

Should an infant experiences one of the conditions listed below, the Investigator will postpone further vaccination until the condition is resolved. Postponement must still be within the timeframe for vaccination indicated in the Table of Study Procedures.

- 1) Febrile illness (temperature $\geq 38.0^{\circ}\text{C}$ [$\geq 100.4^{\circ}\text{F}$]) or moderate or severe acute illness / infection on the day of vaccination, according to Investigator judgment
- 2) Receipt of any vaccine (other than the study vaccine[s]) in the 4 weeks preceding the study vaccination or planned receipt of any vaccine from enrollment through the last study Visit in

which SP0202 or Prevnar 13 is injected (V05), except for influenza vaccination or COVID-19 vaccination, which may be received at least 2 weeks before or 2 weeks after any study vaccination. This exception includes monovalent pandemic influenza vaccines and multivalent influenza vaccines, and COVID-19 vaccines, as applicable per local recommendation.

- 3) Long-term systemic corticosteroid therapy (prednisone or equivalent for more than 2 consecutive weeks within the past 3 months preceding the study vaccination)

5.2.7.2 Definitive Contraindications

Toddlers

Not applicable.

Infants

Should a subject experience 1 of the conditions listed below, the Investigator will discontinue vaccination:

- 1) An anaphylactic or other significant allergic reaction to the previous dose of vaccine
- 2) Receipt of immunosuppressive therapy, such as anti-cancer chemotherapy or radiation therapy
- 3) Ongoing clinical AE related to the previous study vaccination, and in the Investigator's opinion, contraindicating further vaccination
- 4) SAE related to the study vaccine following the previous study vaccination

Subjects with a definitive contraindication will continue to be followed up for the study-defined safety and immunogenicity assessments, as applicable.

In the event of a local or national immunization program with a pandemic influenza vaccine or a COVID-19 vaccine, subjects who receive pandemic influenza vaccine or COVID-19 vaccine at any time during the study will not be withdrawn from the study.

The following AEs constitute absolute contraindications to subsequent vaccinations, according to their respective Product Information. If a subject should experience any of these events during the study, irrespective of causality, that subject is not to receive any additional study vaccines but should continue in the study and be followed up for safety only, as per protocol. Only the vaccine which has a related SAE or a definite contraindication will be stopped wherever it is possible to identify the vaccine that caused the event.

Prevnar

- 1) Hypersensitivity to the active substances, to any of the excipients, to diphtheria toxoid, or to a previous dose of Prevnar 13

Pentacel

- 1) Severe allergic reaction (eg, anaphylaxis) after a previous dose of Pentacel, any ingredient of Pentacel, or any other diphtheria toxoid, tetanus toxoid, pertussis-containing vaccine, inactivated poliovirus vaccine or *H. influenzae* type b vaccine
- 2) Encephalopathy within 7 days of a previous pertussis-containing vaccine with no other identifiable cause
- 3) Progressive neurologic disorder including infantile spasms, uncontrolled epilepsy, or progressive encephalopathy until a treatment regimen has been established and the condition has stabilized

ENGERIX-B

- 1) Severe allergic reaction (eg, anaphylaxis) a previous dose of any hepatitis B-containing vaccine, or to any component of ENGERIX-B, including yeast

RotaTeq

- 1) Demonstrated history of hypersensitivity to the rotavirus vaccine or any component of the vaccine
- 2) History of Severe Combined Immunodeficiency Disease (SCID)
- 3) Episode of intussusception

M-M-R_{II}

- 1) Hypersensitivity to any component of the vaccine, including gelatin
- 2) Anaphylactic or anaphylactoid reactions to neomycin
- 3) Febrile respiratory illness or other active febrile infection
- 4) Patients receiving immunosuppressive therapy. This contraindication does not apply to patients who are receiving corticosteroids as replacement therapy, eg, for Addison's disease
- 5) Individuals with blood dyscrasias, leukemia, lymphomas of any type, or other malignant neoplasms affecting the bone marrow or lymphatic systems
- 6) Primary and acquired immunodeficiency states, including patients who are immunosuppressed in association with acquired immune deficiency syndrome (AIDS) or other clinical manifestations of infection with human immunodeficiency viruses; cellular immune deficiencies; and hypogammaglobulinemic and dysgammaglobulinemic states
- 7) Individuals with a family history of congenital or hereditary immunodeficiency, until the immune competence of the potential vaccine recipient is demonstrated

VARIVAX

- 1) History of severe allergic reaction to any component of the vaccine (including neomycin and gelatin) or to a previous dose of varicella vaccine
- 2) History of primary or acquired immunodeficiency states, leukemia, lymphoma or other malignant neoplasms affecting the bone marrow or lymphatic system, AIDS, or other clinical manifestations of infection with HIV

- 3) Individuals receiving immunosuppressive therapy, including individuals receiving immunosuppressive doses of corticosteroids
- 4) Any febrile illness or active infection, including untreated tuberculosis

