- 6) Complete the end of study CRF of the CRB.
- 7) Provide the memory aid to the subject's parent / guardian.

Safety Follow-up Telephone Call (D180 + 14 days)

The investigator or authorized designee will:

1) Ask to the parent / guardian if the subject has experienced any SAE or AESI in the time since vaccination.

2) Complete the relevant CRF for this phone contact.

A follow-up visit can be arranged depending on the information recorded during the phone call.

Infants

Visit 1 (Day 0): Inclusion, Randomization, Blood Sample, and Vaccination

- 1) Give the subject's parent / guardian information about the study, answer any of her / his questions, obtain written informed consent, and give her / him a signed copy.
- 2) Obtain significant medical history about the subject.
- 3) Check vaccination history.
- 4) Obtain demographic data.
- 5) Check medications and record reportable medication ongoing at the time of inclusion.
- 6) Check inclusion and exclusion criteria for eligibility.
- 7) Conduct a physical examination, including, but not limited to, examination of the head (ear, nose, and throat), neck, heart, lungs, abdomen, and extremities. If a routine examination had been performed within the past week by a qualified health care provider, it does not need to be repeated unless there were changes in health status, in which case it may be limited to the affected area.
- 8) Take the subject's temperature. If the temperature is $\geq 38.0^{\circ}\text{C}$ / $\geq 100.4^{\circ}\text{F}$, postpone vaccination until the condition is resolved.
- 9) If the subject is eligible, contact the IRT for randomization, to obtain a subject number, and vaccine allocation.
- 10) Administer the following study vaccines. Each vaccine should be administered in an assigned location (see Operating Guidelines) and documented appropriately:

Table 5.3: Vaccinations and route of administration at V01, V02, and V03

Vaccine		Route of administration
SP0202 or Prevnar 13	Observer-blind but double-blind across SP0202	Inject IM into the anterolateral area of the thigh, preferably the right thigh
Pentacel	Open-label	Inject IM into the anterolateral area of the thigh , preferably the left thigh (ie, the opposite leg from that used for SP0202 or Prevnar)
ENGERIX-B	Open-label	Inject IM into the anterolateral area of the thigh , preferably the left thigh (ie, the opposite leg from that used for SP0202 or Prevnar)
RotaTeq	Open-label	Administer orally per instructions in the package insert

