6.2 Identity of Other Products

6.2.1 Identity of Other Product 1

Pentacel (Diphtheria and Tetanus Toxoids and Acellular Pertussis Adsorbed, Inactivated Poliovirus and *Haemophilus* b Conjugate (Tetanus Toxoid Conjugate); Sanofi Pasteur Ltd, Toronto, Ontario, Canada

Form: Liquid

Dose: 0.5 mL

Route: IM

Batch Number: Commercial Lot

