CRB: A type of adverse event that is usually alleviated with additional therapeutic intervention. The event interferes with usual activities of daily living, causing discomfort but poses no significant or permanent risk of harm to the research participant.

DC / eDC: Some interference with usual activities.

- Grade 3

CRB: A type of adverse event that interrupts usual activities of daily living, or significantly affects clinical status, or may require intensive therapeutic intervention.

DC / eDC: Significant; prevents usual activities.

- Whether the AE was related to the investigational product (for unsolicited systemic AEs)

The Investigator will assess the causal relationship between the AE and the investigational product as either “Not related” or “Related”, as described in [Section 9.1.1.3.5](#).

- Action taken for each AE (eg, medication)

The action(s) taken by the parent or guardian to treat and/or manage any unsolicited AEs will be classified in the CRB using the following list (all applicable items should be checked):

- None
- Medication
- Health care provider contact
- Hospitalized
- Discontinuation of study vaccination
- Whether the AE was serious
- Whether the AE caused study discontinuation

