9.1.1.3.5 Assessment of Causality

The Investigator will assess the *causal relationship* between each unsolicited systemic AE and the investigational product administered as either *not related* or *related*, based on the following definitions:

Not related – The AE is clearly / most probably caused by other etiologies such as an underlying condition, therapeutic intervention, or concomitant therapy; or the delay between vaccination and the onset of the AE is incompatible with a causal relationship; or the AE started before the first vaccination (screening phase, if applicable)

Related – There is a “reasonable possibility” that the AE was caused by the investigational product administered, meaning that there is evidence or arguments to suggest a causal relationship

Note: By convention, all AEs reported at the injection site (whether solicited or unsolicited) and all solicited systemic AEs are considered to be related to the administered product and therefore are referred to as reactions and do not require the Investigator’s opinion on relatedness.

Adverse events likely to be related to the product, whether serious or not, that persist at the end of the study will be followed up by the Investigator until their complete disappearance or the stabilization of the subject’s condition. The Investigator will inform the Sponsor of the date of final disappearance of the event or the date of “chronicity” establishment.

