#### **4.3.1.3.5 Causal Relationship**

This information will be summarized as collected in the field “Relationship to Investigational Product”. Missing causal relationship will be handled as described in Section 5.3.1.2. Relationship to non-investigational product (ie, Concomitant vaccines) is collected for the Unsolicited Injection Sites Reactions and be presented in summary tables and in the listings. Relationship to study procedure for SAE is only presented in the listings.

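### Protocol 5.2.7.2 conflicts with itself on which vaccines stop, and what follow-up continues, after a listed event in an infant

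*Protocol*

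**What the plan says.** Protocol 5.2.7.2 (Definitive Contraindications, infants) has two parts. The first lists four general conditions that end vaccination and says that subjects with a definitive contraindication stay in follow-up for safety and immunogenicity, as applicable. The second lists events by product (Prevnar, Pentacel, ENGERIX-B, RotaTeq, M-M-R II, VARIVAX) and puts two sentences in front of the list:

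- An infant with a listed event is covered thus: "irrespective of causality, that subject is not to receive any additional study vaccines". The same sentence keeps the infant in the study for safety follow-up only.
- Immediately afterwards, speaking of the vaccine responsible for the event: "Only the vaccine which has a related SAE or a definite contraindication will be stopped wherever it is possible to identify the vaccine".

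The causality records are described elsewhere. Protocol 9.1.1.3.5 has the investigator judge the relationship "between each unsolicited systemic AE and the investigational product administered as either" not related or related. Protocol 10.4 applies the same assessment to SAEs and adds relationship to study procedures. The co-administered vaccines are not investigational products; they come under Protocol 6.2, "Identity of Other Products". SAP 4.3.1.3.5 states: "Relationship to non-investigational product (ie, Concomitant vaccines) is collected for the Unsolicited Injection Sites Reactions".

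Protocol 12.2.3 excludes from PPAS2 and PPAS3 any subject whose vaccination schedule was not completed. SAP 5.2.1 adds up to V03 and up to V05 respectively, but neither document says which vaccines make up the schedule.

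**The concern.** One sentence disregards cause and the next depends on it. A site that follows the first literally ends the pneumococcal vaccine (PCV) series after an event listed under another product. A site that follows the second ends only the other product. The section also gives two scopes of follow-up, one with immunogenicity and one without.

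Between them, these sentences decide whether the infant receives later PCV doses and gives later blood samples. They therefore decide whether the infant enters the per-dose safety tables for those doses, and they bear on the immunogenicity analysis sets. With about 52 sites planned (42 + 8 + 2), uniform handling cannot be assumed when the text supports more than one course. The infants concerned are also those whose records will be read most closely.

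**Working it through.** No figure in the plan needs to be reproduced. The check is to set the sentences side by side and follow one infant through them.

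**1. Scope of the stop-all sentence.** At the infant visits the protocol uses the term study vaccines broadly: "Administer the following study vaccines. Each vaccine should be administered in an assigned location" introduces Table 5.3, which lists SP0202 or Prevnar 13, Pentacel, ENGERIX-B and RotaTeq. Protocol 5.1.1 elsewhere contrasts study vaccines with concomitant pediatric vaccines. The conflict over the PCV survives either usage, because the PCV is a study vaccine under both.

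**2. Overlap of the two follow-up sentences.** The two scopes could be kept apart if they governed different events, but they do not. An anaphylactic reaction to a previous dose is in the general list, and severe allergic reaction is in the Pentacel and ENGERIX-B lists. Both lists stand under the heading of definitive contraindications.

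**3. One infant: intussusception after V01, attributed by the investigator to RotaTeq.** The event is listed under RotaTeq alone.

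| Text applied | PCV at V02, V03, V05 | Blood at V04, V05, V06 | Consequence |
|---|---|---|---|
| Stop-all sentence, safety follow-up only | No | No | Absent from safety denominators after Doses 2 to 4; no V04 or V06 result, so outside FAS2, PPAS2, FAS3 and PPAS3 |
| Stop-all sentence, with the earlier follow-up sentence | No | Yes, as applicable | Absent from safety denominators after Doses 2 to 4; in FAS2 if V04 gives a valid result (one primary-series dose suffices); outside PPAS2 (schedule incomplete) and FAS3 (no booster dose) |
| Single-vaccine sentence, immunogenicity follow-up continuing | Yes | Yes | In the safety denominators after Doses 2 to 4; in FAS2 and FAS3 if results are valid; PPAS2 and PPAS3 depend on whether missed RotaTeq doses make the schedule incomplete, which is not stated |

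The FAS entries use the definitions in Protocol 12.2.1 and the PPAS entries those in 12.2.3.

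**4. Whether the single-vaccine sentence can be traced in the data.** Which vaccines were later given can be recovered. Protocol 5.1.4 has injection details and dose number recorded, 5.1.2 has ENGERIX-B documented in the eCRF, and 6.3.2.3 has the dose given to each subject logged and label information entered in the CRB. The vaccine judged causal is a different matter. For an unsolicited systemic event the documents describe relationship to the investigational product, plus study procedures for SAEs. They mention relationship to concomitant vaccines only for unsolicited injection site reactions. Intussusception, encephalopathy and anaphylaxis are systemic events.

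**5. Size.** The conflict can change later doses after V01, V02 or V03, since each of those visits is followed by another PCV dose. The documents give no rate for the listed events. Per affected infant the shift is 1/175 = 0.6% of a planned group, 1/140 = 0.7% of those expected evaluable post-Dose 3, or 1/122 = 0.8% post-Dose 4.

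**The case against.** The best defence is that the stop-all sentence is a default and the single-vaccine sentence an exception for cases where the cause can be identified. The second sentence carries its own condition, and the events are listed product by product, which gives a site some basis for reading it that way. But nothing in the wording joins the sentences as rule and exception, and a default that sets cause aside cannot be narrowed by cause without saying so. The defence also leaves the two follow-up scopes unreconciled.

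Other parts of the defence stand, and they limit what a reader might infer:

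- That a vaccine known to have caused the event might be continued. Neither sentence allows this; the dispute is over the remaining vaccines.
- That the data cannot show what was stopped. The dose records should show it.
- That the CRF has no item for concomitant-vaccine causality in systemic events. The CRF, its completion instructions and the Operating Guidelines are not among the documents, so this can only be inferred from what the protocol and SAP describe.
- That every event caused by a co-administered vaccine is lost as not related. Under Protocol 9.1.1.3.5 that category needs another cause to be clear or most probable; a reasonable possibility of the PCV makes the event related.
- That the per-protocol sets must change. They may not: if missed RotaTeq doses make the schedule incomplete, the infant leaves PPAS2 under every row of the table.

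**Conclusion.** The contradiction is real and should be corrected. Read literally, Protocol 5.2.7.2 supports different remaining vaccination and different follow-up for the same infant. The effect on safety denominators for later doses is direct. The effect on FAS2 and FAS3 depends on which doses are given and whether blood is drawn, and the effect on PPAS2 and PPAS3 cannot be settled until the completed-schedule criterion is defined.

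The numerical effect is probably very small, on the assumption that the listed events are rare in healthy infants; the documents give no rate to test this. A reader might go further and infer that the description of safety by group, a primary objective, is weakened. The documents do not support that. The endpoints are occurrences of events rather than reasons for stopping, the Stage II groups are randomized with the same planned routine schedule, and no hypothesis is tested. The case for correction rests on uniform handling of a few infants with serious events. This point takes no view on which stopping rule or follow-up is right.

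**What to change.** 1. Replace the conflicting sentences in Protocol 5.2.7.2 with one instruction that says which vaccines stop and what follow-up applies, for the general list and the product-specific list alike. The clinical content is for the sponsor to decide.
2. State in Protocol 12.2.3 and SAP 5.2.1 whether stopping only a concomitant vaccine counts as not completing the vaccination schedule for PPAS2 and PPAS3.
3. If the reconciled rule depends on identifying the causal vaccine, record the vaccine judged causal for SAEs, AESIs and AEs leading to discontinuation of vaccination. First check whether the CRF already does so. A separate field for the vaccines stopped is not needed, since this can be derived from the dose records.

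The cost is a paragraph of protocol wording and a line in each per-protocol definition. Under item 3 there is one further CRF item, completed for a small number of events.
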